## 7.2 Disposition of Subjects

Subject demographics and reasons for screening failure will be summarized for screen-failed subjects.

Subjects (n and %) who completed or discontinued from the study will be tabulated by treatment group and for all 3 groups combined. The primary reasons for study discontinuation will be included in the tabulation. The primary reasons may include, but not limited to, any of the following:

- Subject withdrew consent
- Lost to follow-up
- Administrative reason
- Adverse event
- Investigator decision
- Failure to follow required study procedures
- Other

Subject disposition will be summarized for all enrolled subjects. Subject counts for the Safety and PP populations will be included in the table. A data listing for subject disposition will be presented for all enrolled subjects.

## 7.3 Protocol Deviations

Protocol deviations will include, but are not limited to

- Non-compliance with any scheduled study visit
- Non-compliance with study treatment
- Received prohibited medications (see Protocol Section 8.1)
- Non-compliance with study inclusion or exclusion criteria
- Non-compliance with study assessment procedures

Subjects with major protocol deviations will be listed. The listing will include a brief description of the deviation, deviation category, and if applicable, study day when deviation occurred along with other pertinent information.

If warranted by the sample size, subjects (n and %) with major protocol deviations will be tabulated by treatment group and by deviation category.

Subjects (n and %) will be tabulated by treatment group for each analysis population. Subjects who are excluded from the PP population will be listed with reasons for exclusion.

#### **7.4 Demographics and Baseline Subject Characteristics**

Descriptive statistics for subject characteristics and baseline values will be presented for all populations by treatment group and for all 3 groups combined. Continuous variables will be summarized with n, mean, SD, and median. Categorical variables will be summarized with n and % of subjects for each category, for the Safety and PP populations.

#### **7.5 Baseline Disease Characteristics**

Baseline disease characteristics will be included in the subject data listing.

#### **7.6 Medical History**

Subject incidence (n and %) of medical history (and current medical condition before signing the informed consent) will be tabulated by MedDRA System Organ Class (SOC) and Preferred Term (PT).

#### **7.7 ECG**

A listing of ECG overall interpretation at screening visit will be provided.

#### **7.8 Pregnancy Test**

A listing of pregnancy test results will be provided.

#### **7.9 Treatments**

##### **7.9.1 Treatment Compliance and Extent of Exposure**

Summaries of treatment compliance and exposure to AK002 will be based on the safety population.

Duration of treatment exposure is defined as the total number of days a subject is exposed to the study treatment. This will be calculated for each subject by taking the difference between the date of the last dose minus the date of the first dose, plus 1 (date of last dose – date of first dose +1).

Duration of exposure will be summarized using descriptive statistics (n, mean, standard deviation, median, minimum, and maximum).

Treatment compliance is defined as the number of infusions subjects received divided by 4 (i.e., total number of infusions expected)  $\times$  100%. Treatment compliance will be summarized descriptively. In addition, an overall compliance that includes adherence to treatment administration schedule and any interruptions will be included in the data listing.

The treatment infusion information (length, volume, rate, and interruption) will be included in the subject data listing.

### 7.9.2 Prior and Concomitant Medications

Prior medications and concomitant medications will be extracted from the Prior/Concomitant Medication CRF. Medications taken prior to Study Day 1 will be considered as prior medications and medications taken on or after Study Day 1 will be considered as concomitant medications. Prior and concomitant medications will be coded using WHO Drug Dictionary (WHODD March 2018 release) for Preferred Term (PT) and Anatomical Therapeutic Chemistry (ATC) classification.

Prior and concomitant medications will be tabulated separately based on the Safety Population. The number (n and %) of subjects taking at least one medication and the number (%) of subjects taking each medication at the preferred term level will be tabulated by ATC4, and PT. Subjects taking the same PT medication twice will only be counted once.

A subject data listing will be provided to include the reported medication name, the WHODD PT, ATC4, study day and pertinent subject information.

A separate data listing will include subjects who have received prohibited medications.

## 7.10 Analysis of Primary Efficacy Endpoint

### 7.10.1 Primary Analysis of Primary Efficacy Endpoint

The primary efficacy endpoint is the percent change from baseline to Day 99 in the number of eosinophils per HPF in gastric or duodenal mucosa with biopsy. For subjects who provide gastric or duodenal only biopsy, the calculation will be based on the average count of the highest readings from the respective mucosa at baseline and Day 99. For subjects who provide both gastric and duodenal biopsies, the calculation will be based on the average count of the highest readings from the Day 99 biopsy that correspond in location (gastric or duodenal) to the location with the highest average count at baseline. This endpoint will be summarized by treatment group.

The pooled high/low dose group and each active dose group will be compared to the placebo group in pairwise comparison using analysis of covariance (ANCOVA) model with percent change from baseline as outcome, treatment as factor, and baseline value and randomization stratum as covariates. To control for the type-I error, the Gatekeeping procedure defined in Section 6.8 will be followed.

#### 7.10.2 Secondary Analysis of Primary Efficacy Endpoint

In this analysis, percent change from baseline will be analyzed by the Cochran-Mantel-Haenszel  $\chi^2$  (chi-square) test for the row mean score difference stratified by the randomization stratification variable. A sample SAS code for the pairwise comparison is as follows.

```
PROC FREQ ;
  WHERE TRTP IN ('GRP1','PBO') ;
  TABLES RANDSTRA*TRTP*PCHG / CMH SCORE=MODRIDIT RISKDIFF(CL=NEWCOMBE) ;
  ODS OUTPUT CMH=CMHPVAL(WHERE=(ALTHYPOTHESIS='Row Mean Scores Differ')) ;
RUN ;
```

#### 7.10.3 Sensitivity Analyses of Primary Efficacy Endpoint

##### Sensitivity Analysis

In this analysis, a responder is defined as an eosinophil count  $<30$  cells/HPF. Subjects with missing eosinophil count will be considered non-responders. A logistic regression model with effects of treatment group, randomization stratum, and baseline eosinophil count will be used to analyze the between group difference. Odds ratio and the associated 95% confidence intervals are computed for the comparison of odds of achieving response in the active treatment group against the odds in the placebo group. A sample SAS code:

```
PROC LOGISTIC ;
  CLASS group stratum / PARAM=glm ;
  MODEL resp(REF='0')=group stratum base ;
  ESTIMATE 'Grp 1 - Grp 3' group 1 0 -1 ;
  ESTIMATE 'Grp 2 - Grp 3' group 0 1 -1 ;
  ESTIMATE 'Avg Grp1,2 - Grp 3' group 0.5 0.5 -1 ;
  ODS OUTPUT ESTIMATES=parmest ;
RUN ;
```

In addition to the responder analysis, a cumulative distribution function (CDF) will be plotted for the 3 treatment groups, where the horizontal axis is the change from baseline in eosinophil count (x), ranging from the smallest (negative value meaning reduction) to the largest (positive value meaning increase) observed in the trial, and the vertical axis is the percentage of patients whose eosinophil count is  $\leq x$  cells/HPF.

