#### **3.2.3 Methods of Assigning Subjects to Treatment Group**

Approximately 60 subjects will be stratified based on the highest weekly average of the qualifying symptom of disease recorded on the PRO questionnaire during the screening period (PRO score 3–4.9, or 5.0–10.0) and randomized in a 1:1:1 ratio to Treatment Groups 1, 2, and 3 (Section 3.2.1).

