### 3.5 Determination of Sample Size

Assuming a reduction of 30% in the number of eosinophils per HPF (primary endpoint) from baseline in the AK002-treated group (Treatment Group 1 or 2) versus a 10% reduction per HPF in the placebo group (Treatment Group 3), and assuming a standard deviation of 20%, 20 subjects per group would provide 87% power with a significance level of 0.05.

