## **6.8 Multiple Comparisons/Multiplicity Adjustment**

To control for the family-wise type-I error rate, the following testing procedures will be implemented:

1. Test the high/low dose (Treatment Groups 1 and 2) combined group against placebo (Treatment Group 3) for the primary efficacy endpoint. If  $p \leq 0.05$  then proceed to
2. Test the high/low dose combined group against placebo for the 1st secondary efficacy endpoint. If  $p \leq 0.05$  then proceed to
3. Test the high/low dose combined group against placebo for the 2nd secondary efficacy endpoint. If  $p \leq 0.05$  then proceed to
4. Test the high dose against placebo for the primary efficacy endpoint. If  $p \leq 0.05$  then proceed to

5. Test the low dose against placebo for the primary efficacy endpoint. If  $p \leq 0.05$  then proceed to
6. Repeat above Steps 4-5 for testing the 1st secondary efficacy endpoint, then the 2nd secondary efficacy endpoint.

In the above sequential testing, if any step has  $p > 0.05$  then the tests of this step and of all subsequent steps will be considered not statistically significant.

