### 7.11.1 Treatment Responder at End of Study Treatment

Proportion of patients with a >30% reduction in TSS combined with a >75% reduction in eosinophils in the gastric and/or duodenal mucosa will be analyzed using the logistic regression model similar to Section 7.10.2 Sensivity Analysis. The calculation of the TSS score is found in Section 5.2 1st Secondary Endpoint.

As an exploratory analysis, the analysis of the treatment responder will be repeated for select subgroups (Section 6.9) such as EG, EGE, and EG + EGE. For each subgroup, separate logistic regression analysis will be performed similar to the sensitivity analysis for the primary endpoint of Section 7.10.3. In the analysis, two active dose groups will be combined for the comparison to the placebo group.

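### Step 2 of the testing order calls for the two doses combined against placebo, but the only logistic code averages the two doses' log-odds: a different comparison, which fails if an active arm has all or no responders

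*SAP*

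**What the plan says.** - **Section 6.8, step 2:** "Test the high/low dose combined group against placebo for the" first secondary endpoint, which is the responder endpoint. A p-value above 0.05 at any step makes that step and all later ones non-significant.
- **Section 7.11.1** sends this endpoint to a logistic regression similar to a sensitivity analysis that it cites as Section 7.10.2. Section 7.10.2 is a Cochran-Mantel-Haenszel test. The logistic model is in 7.10.3.
- **Section 7.10.3** gives sample code with a three-level treatment variable, stratum and baseline, fitted by ordinary maximum likelihood. Its line for both doses is "ESTIMATE 'Avg Grp1,2 - Grp 3' group 0.5 0.5 -1". No Firth or exact option appears.
- **Two passages give context only.** Section 7.10.1 says "The pooled high/low dose group and each active dose group will be compared to the placebo group", but this is for the ANCOVA of the primary endpoint. Section 7.11.1 says "two active dose groups will be combined for the comparison to the placebo group", but this is for the exploratory subgroup analyses.

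No section says whether the combined comparison at step 2 is one pooled arm or an average of two arms.

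**The concern.** Combining two arms and averaging their log-odds are different operations. Pooling 20 + 20 subjects gives one response rate and one log-odds. The sample code takes the log-odds of each arm and averages them. On the logit scale these differ whenever the arms differ, and the averaged version takes much of its variance from whichever arm is nearest 0% or 100%. If an active arm has all or no responders, its log-odds is infinite and the averaged Wald test gives p near 1, whatever the other arm shows.

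A programmer following the text and one following the code could therefore report different results at step 2. That step decides whether the pooled TSS test and every single-dose test, including those on the primary endpoint, can be declared significant.

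**Working it through.** **The plan's own figure.** Section 3.5 says "20 subjects per group would provide 87% power with a significance level of 0.05", for 30% v 10% reduction and "assuming a standard deviation of 20" percent. A two-sided two-sample t-test with 38 df and noncentrality (20/20) × √(20/2) = 3.16 gives 86.9%, so the 87% is reproduced. It covers the primary endpoint for a single dose. The SAP gives no response rates and no power for the responder endpoint, so every rate below is an assumption.

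**Inputs.** About 60 subjects, "randomized in a 1:1:1 ratio to Treatment Groups 1, 2, and 3" (3.2.3), hence 20 per arm and 40 v 20 when pooled. Alpha is 0.05, taken as two-sided because the SAP does not state sidedness.

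**Formulas, without covariates.** Let a, b and c be the responders in the high, low and placebo arms.

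- Averaged: estimate = ½ logit(a/20) + ½ logit(b/20) − logit(c/20); variance = ¼[1/a + 1/(20−a)] + ¼[1/b + 1/(20−b)] + 1/c + 1/(20−c).
- Pooled, with m = a + b: estimate = logit(m/40) − logit(c/20); variance = 1/m + 1/(40−m) + 1/c + 1/(20−c).

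**One data set, two answers (14, 2 and 2 responders).**

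- Averaged: ½(0.847) + ½(−2.197) + 2.197 = 1.522, odds ratio 4.58. Variance 0.0595 + 0.1389 + 0.5556 = 0.7540, SE 0.868, z = 1.75, p = 0.080.
- Pooled: 16/40 v 2/20, odds ratio (16/24)/(2/18) = 6.00, log 1.792. Variance 0.0625 + 0.0417 + 0.5556 = 0.6597, SE 0.812, z = 2.21, p = 0.027.

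The hierarchy stops under one version and continues under the other.

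**An all-responder arm (20, 12 and 2 responders).** The averaged contrast has SE about 8,884 and p = 0.999. Pooled, 32/40 v 2/20 gives odds ratio 36, log 3.58, SE √(1/32 + 1/8 + 1/2 + 1/18) = 0.84 and p = 0.00002.

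**Power.** All 21³ outcomes were enumerated exactly. A fit that cannot be estimated counts as not significant.

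| High/low/placebo | Averaged | Pooled |
|---|---|---|
| 50/50/10% | 78.1% | 78.3% |
| 70/50/20% | 86.1% | 86.6% |
| 60/40/10% | 77.4% | 78.6% |
| 50/30/10% | 50.9% | 53.5% |
| 70/30/20% | 56.5% | 62.5% |
| 60/20/10% | 42.6% | 54.1% |
| 60/10/10% | 14.9% | 35.0% |
| 90/30/20% | 75.0% | 88.3% |
| 95/60/30% | 62.3% | 96.1% |
| 95/95/20% | 40.7% | 86.1% |

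Pooling does not gain power by inflating the type I error: with all three rates at 30% the tests reject in 4.3% and 4.2% of trials.

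**Separation.** The chance that at least one active arm is all or none is 12% at 90/30/20%, 36% at 95/60/30% and 59% at 95/95/20%. An empty placebo arm breaks both versions. Its chance at a 10% placebo rate is 0.9²⁰ = 12%.

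**Check with covariates.** A simulation of 3,000 trials per scenario, with a stratum and a baseline covariate in the model, gives the same pattern: 70/50/20%, 83.9% v 83.6%; 60/10/10%, 18.8% v 37.5%; 95/60/30%, 62.6% v 94.7%, with 35% v 0.2% of fits not converging.

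**The case against.** **A reader might infer that the averaged contrast loses power whenever the doses differ.** It does not. In the scenarios with a 20-point difference above, the loss is 0.5 to 2.6 points. If trials with an all-or-none arm are set aside, the averaged contrast can be slightly stronger (90/50/30%: 89.1% v 86.0%; 95/60/30%: 97.2% v 95.2%). Section 3.5 assumes the same reduction for either dose. If equal dose effects carried over to the responder endpoint, at rates away from 0% and 100%, the choice would hardly matter.

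**A reader might infer that the plan fixes the wrong estimator at step 2.** It does not go that far. The code is labelled a sample, belongs to a sensitivity analysis of the primary endpoint, and reaches step 2 only by similarity and a wrong section number. The defect is a conflict left open. Within 7.10.3 the contrast is labelled as an average, which it is, so changing it there is for consistency.

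**A reader might take the combining sentence in 7.11.1, or the pooled wording in 7.10.1, as direct contradictions.** The first governs exploratory subgroups and the second an ANCOVA. The conflict rests on 6.8 against the 7.10.3 code.

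**A reader might carry the near-100% losses over to the gate.** These rates are most plausible for the <30 cells/HPF analysis, which is outside the hierarchy. The responder endpoint needs both a symptom and a histological reduction, and nothing in the SAP suggests that an arm of 20 responders out of 20 is likely there.

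What is left is a gating test with two readings that can fall on opposite sides of 0.05, and one of them fails on data that the other handles.

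**Conclusion.** The concern holds in this limited form. Section 6.8 names a combined group, while the only logistic code tests a mean of two log-odds. The consequence at step 2 is negligible for equal or moderately different doses. It is material, about 11 to 20 points of power, when the low dose is at or near a 10% placebo rate (60/20/10% and 60/10/10%). An active arm near 0% or 100% adds the risk that the averaged contrast cannot be estimated at all, and the near-100% case is mainly a matter for the <30 cells/HPF analysis.

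These sizes rest on assumed response rates, 20 evaluable subjects per arm, two-sided Wald tests and, for the main table, no covariates. The mismatch between text and code rests on none of these. It should be resolved before unblinding, because afterwards the choice could be made with the result in view.

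**What to change.** 1. In 7.11.1, state that the step 2 comparison uses a two-level treatment term (Groups 1 and 2 combined v Group 3) with stratum and baseline, as 6.8 implies. Use the same term for the pooled comparison in 7.10.3, for consistency, in place of the 0.5/0.5/−1 line.
2. Keep the three-level model for the single-dose contrasts.
3. Correct the reference in 7.11.1 from 7.10.2 to 7.10.3.
4. Name a penalised (Firth) or exact method, and when it applies, for arms with all or no responders. Pooling alone does not help when placebo has no responders.

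The cost is one extra model call and a few sentences. In the equal-dose scenarios above, pooling loses no power. If the sponsor does intend the averaged contrast, 6.8 should say so, and item 4 becomes more important.

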## 7.11 Analysis of Secondary Efficacy Endpoints

A cumulative distribution function (CDF) plot will be generated for the 3 treatment groups for the percent changes from baseline in the TSS scores averaged over the 14 daily scores starting with the day of the last dose to the day before the end of the study biopsy. (See Section 5.2 for detail of the calculation.)

### 7.11.1 Treatment Responder at End of Study Treatment

Proportion of patients with a >30% reduction in TSS combined with a >75% reduction in eosinophils in the gastric and/or duodenal mucosa will be analyzed using the logistic regression model similar to Section 7.10.2 Sensivity Analysis. The calculation of the TSS score is found in Section 5.2 1st Secondary Endpoint.

As an exploratory analysis, the analysis of the treatment responder will be repeated for select subgroups (Section 6.9) such as EG, EGE, and EG + EGE. For each subgroup, separate logistic regression analysis will be performed similar to the sensitivity analysis for the primary endpoint of Section 7.10.3. In the analysis, two active dose groups will be combined for the comparison to the placebo group.

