### **3.4 Hypotheses**

The hypothesis to be tested in the study is that AK002, in either one or both of the 2 doses, are different from placebo with regard to the primary endpoint of number of eosinophils per HPF in biopsies from the gastric mucosa.

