Dates will be presented in the ISO-8601 format YYYY-MM-DD. Times will be displayed in 24-hour clock format. Numbering for tables, figures and listings will follow ICH E3 Guideline (ICH, 1996).

Alternative methods of analysis of the data may be considered prior to database lock should some of the assumptions underlying the proposed analyses not be met. Reason for departure from the planned methods will be documented as an amendment to the SAP or in the CSR.

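### If no placebo subject responds, the logistic Wald test planned for the responder endpoint cannot reach significance, and the TSS test and all dose-specific tests close with it

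*SAP*

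**What the plan says.** SAP Section 7.11.1 states that the responder proportion "will be analyzed using the logistic regression model similar to Section 7.10.2 Sensivity Analysis". Section 7.10.2 contains no logistic model; there, "percent change from baseline will be analyzed by the Cochran-Mantel-Haenszel" row-mean-score test. The logistic model is in Section 7.10.3. Its sample code is PROC LOGISTIC with treatment group, randomisation stratum and baseline count, with no Firth option and no exact statement. The pooled comparison is the line "ESTIMATE 'Avg Grp1,2 - Grp 3' group 0.5 0.5 -1".

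Section 6.8 puts the pooled responder test at step 2. Step 3 is pooled TSS, steps 4 and 5 are the high and low dose on the primary endpoint, and step 6 repeats the dose tests for both secondary endpoints. If any step has p > 0.05, "then the tests of this step and of all subsequent steps will be considered not statistically significant".

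Section 5.2 requires a responder to have both a TSS reduction above 30% and an eosinophil reduction above 75%. Section 6.1 adds a general clause: "Alternative methods of analysis of the data may be considered prior to database lock". For the exploratory subgroups, Section 7.11.1 says: "For each subgroup, separate logistic regression analysis will be performed similar to the sensitivity analysis for the primary endpoint".

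**The concern.** With no responders in the placebo arm, the placebo log-odds have no finite maximum-likelihood estimate. The fitted value moves off by about one unit per iteration while its standard error grows exponentially. The Wald ratio therefore shrinks towards zero and p rises towards 1. The reported p-value reflects when the software stopped, not the strength of the evidence.

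This happens when placebo does worst, and it costs most when the drug works well. A large responder effect would be reported as not significant, and steps 3 to 6 would be closed however strong their own results. Step 1, the pooled primary endpoint, is not affected.

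**Working it through.** **The plan's own figure.** SAP Section 3.5 says "20 subjects per group would provide 87% power with a significance level of 0.05", for reductions of 30% against 10% with SD 20%. Section 3.4 ("are different from placebo with regard to the primary endpoint") is read as two-sided. The standardised difference is (30 − 10)/20 = 1. A two-sided two-sample t-test with 20 per group then has 86.9% power, which reproduces the stated figure. It covers the primary endpoint only; the SAP gives no responder rates and no power for step 2.

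**Inputs.** Allocation is 1:1:1 with about 60 subjects (Section 3.2.3), so step 2 compares 40 with 20. The model and contrast are those of Section 7.10.3.

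**The Wald test with 0/20 on placebo.** Without covariates, each arm has log-odds θ with variance v = 1/[n p(1 − p)]. The contrast is 0.5θ₁ + 0.5θ₂ − θ₃, with variance 0.25v₁ + 0.25v₂ + v₃. Take 10/20 responders in each dose arm: θ₁ = θ₂ = 0 and v₁ = v₂ = 1/(20 × 0.25) = 0.2, so the active arms contribute 0.1 to the variance. The rest is placebo. Newton iterations from zero give:

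| Iterations | Contrast | SE | z | p |
|---|---|---|---|---|
| 5 | 6.20 | 4.98 | 1.24 | 0.21 |
| 6 | 7.20 | 8.20 | 0.88 | 0.38 |
| 8 | 9.20 | 22.3 | 0.41 | 0.68 |
| 10 | 11.20 | 60.6 | 0.19 | 0.85 |
| 12 | 13.20 | 164.6 | 0.08 | 0.94 |

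On the same data:
- Fisher's exact test gives p = 3.5 × 10⁻⁵.
- Firth's method for the pooled comparison without covariates adds 0.5 to each cell. The odds ratio is (20.5/20.5)/(0.5/20.5) = 41, with 95% profile limits 5.0 to 5342 and penalised-likelihood-ratio p = 2.4 × 10⁻⁵.

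With stratum and baseline in the model, no result from 4/40 to 36/40 against 0/20 reached p ≤ 0.05 at any stopping point tried between 6 and 25 iterations. Even 36/40 against 0/20 gave 0.18 at 6 and 0.55 at 8.

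**One placebo responder restores the test.** Without covariates, 20/40 against 1/20 gives Wald p = 0.006 (Fisher 0.0005). Taking that responder away strengthens the evidence and breaks the planned test.

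**A full dose arm.** For 20/20 and 10/20 against 2/20, the three-group contrast at 8 iterations is 6.80 with SE 11.2, so p = 0.54; Fisher gives 1.7 × 10⁻⁶. At 5 iterations it is 5.30/2.61 = 2.03, p = 0.042, so here the conclusion itself depends on the stopping point. Coded as pooled active against placebo (30/40 against 2/20), the log odds ratio is ln 27 = 3.30, SE = √(1/30 + 1/10 + 1/2 + 1/18) = 0.83 and p = 7 × 10⁻⁵.

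**How often placebo is empty.** P(0/20) = (1 − π)²⁰. The placebo rate π is an assumption.

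| π | 1% | 2% | 5% | 10% | 15% | 20% |
|---|---|---|---|---|---|---|
| P(0/20) | 82% | 67% | 36% | 12% | 4% | 1% |

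**Step-2 power.** These figures come from 8,000 simulated trials per scenario, with 20 per arm, two balanced strata, a non-prognostic baseline covariate, and Wald iteration stopped at convergence or after 8 steps.

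| Active rate | Placebo rate | Wald as planned | Firth | Exact CMH |
|---|---|---|---|---|
| 50% | 2% | 34% | 99.8% | 99.7% |
| 50% | 5% | 61% | 98% | 98% |
| 50% | 10% | 78% | 91% | 90% |
| 50% | 20% | 60% | 62% | 58% |
| 30% | 5% | 22% | 66% | 64% |
| 30% | 10% | 21% | 40% | 37% |

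No simulated trial with an empty placebo arm reached Wald p ≤ 0.05.

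**The case against.** **The SAP never says Wald.** It calls the model similar to another section, gives the code as a sample, and cites a CMH section; Section 6.3 also lists CMH among possible methods. CMH tolerates an empty cell. This has some force, but Section 7.11.1 names logistic regression and a sensitivity analysis, and only Section 7.10.3 fits both. If the ambiguity is real, it makes matters worse: the same data could pass or fail step 2 depending on which half of the sentence is followed.

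**The frequency is assumed.** This stands. At a 20% placebo rate there is practically no loss. Under the planning values of Section 3.5, and assuming normality, an eosinophil reduction above 75% has probability Φ((−75 + 10)/20) = 0.06% on placebo, so 0/20 has probability of about 0.99. On active it is only Φ((−75 + 30)/20) = 1.2%, so no test would then show a difference. The defect costs power only if the active effect is well above plan.

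**A full or empty dose arm is a side issue.** Largely agreed. It arises from the three-group contrast and disappears in step 2 with pooled coding. For an empty dose arm (0/20 and 10/20 against 2/20) the pooled Wald p is 0.19 in any case.

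**Sections 1 and 6.1 allow departures to be documented in the CSR.** That is a reporting route. The choice of alternatives in Section 6.1 is discretionary, names no method and ends at database lock, whereas the empty arm shows only after unblinding. A test chosen then is not pre-specified.

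**Firth is only one option.** True: the exact CMH test has almost the same power. What matters is naming one test that tolerates a zero cell.

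**Conclusion.** The concern holds. Given 0/20 on placebo, the planned test gave p > 0.05 at every stopping point examined, even where exact and penalised tests gave p-values near 10⁻⁵. Section 6.8 then closes steps 3 to 6. At an assumed 50% active rate, step-2 power falls from 98% to 61% at a 5% placebo rate and from 99.8% to 34% at 2%; at 20% the loss is negligible.

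The mechanism is certain; its frequency rests on responder rates the SAP does not give. The iterations were not run in SAS, which may stop elsewhere with a separation warning, so individual Wald p-values are illustrative. The per protocol population used for efficacy may have fewer than 20 placebo subjects, which would make an empty cell more likely. Because one cell can close every later confirmatory test, this must be settled before unblinding.

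**What to change.** In Section 7.11.1, name one test for step 2 and for the responder tests in step 6, to be used whatever the cell counts:

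- Firth-penalised logistic regression with the planned covariates (randomisation stratum and baseline eosinophil count).
- Treatment coded as pooled active against placebo in step 2, and as each dose against placebo in step 6.
- The p-value from the penalised likelihood ratio, with the odds ratio and 95% profile penalised-likelihood limits. The ESTIMATE output should not be used, because a Wald p-value from a Firth fit is still weak: for 12/40 against 0/20 it is 0.059, where Fisher gives 0.005.
- The cross-reference corrected from 7.10.2 to 7.10.3.

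Use the same method for the sensitivity analysis at fewer than 30 cells/HPF and for the subgroup responder models, where empty cells are likelier still. With an assumed 7 placebo subjects, P(0/7) is 70%, 48% and 21% at placebo rates of 5%, 10% and 20%.

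The cost is SAP wording and a procedure option; the covariates stay. Simulated type I error of the pooled Firth test was 0.5%, 1.8%, 3.3%, 4.3%, 4.3% and 4.8% at common responder rates of 2%, 5%, 10%, 20%, 30% and 50%, so 5% was not exceeded.
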